## Per-protocol set (PPS)

Per-protocol set will be comprised of patients in FAS who

- did not have any important protocol deviations
- took at least 80% of randomized study medication(s). If a patient vomited the original dose but did not vomit the replacement dose, the patient is considered as taking the dose of study medication. Except for patients who are assigned to Coartem® cohort, this requires that all patients take all KAF156 and LUM-SDF dosages as assigned
- did not take other antimalarial medications prior to Day 29 for reasons other than rescue medication given for signs and symptoms of infection with *P. falciparum* or unsatisfactory therapeutic effect, and
- met at least one of the following criteria: (a) classified as treatment failure before Day 8 (see [Section 6.5.8](#)), (b) absent from parasitaemia at Day 29 or later, or (c) had valid PCR evaluations at baseline and at the time point with parasitaemia if parasitaemia is present at Day 8 or later.

Important protocol deviations for exclusion from PPS will be identified by the clinical team before database lock for each part.

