2.1.1.1 Definition of treatment failures

Early Treatment Failures (ETF)

Patient will be classified as ETF upon meeting any of the following criterion

- Development of danger signs or severe malaria on Day 2, Day 3, Day 4 in the presence of parasitemia.
- Parasitemia on Day 3 higher than Day 1 count irrespective of axillary temperature.
- Parasitemia on Day 4 with axillary temperature $\geq 37.5^{\circ}\text{C}$.
- Parasitemia on Day 4 equals to or more than 25% of count on Day 1.

Late Clinical Failure (LCF)

Patient will be classified as LCF upon meeting any of the following criterion

- Development of danger signs or severe malaria on any day from Day 5 to Day 43 in the presence of parasitemia without previously meeting any of the criteria of early treatment failure.
- Presence of parasitemia and axillary temperature $\geq 37.5^{\circ}\text{C}$ on any day from Day 5 to Day 43 without previously meeting any of the criteria of Early Treatment Failure.

Late Parasitological Failure (LPF)

- Presence of parasitemia on any day from Day 8 to Day 43 and axillary temperature $< 37.5^{\circ}\text{C}$ without previously meeting any of the criteria of Early Treatment Failure or Late Clinical Failure. Missing body temperature assessment in presence of parasitemia will be classified as LCF.

Note: If the temperature is measured using other routes, such as oral/tympanic/rectal, the corresponding threshold for fever is 38.0°C . Danger signs or severe malaria is recorded as adverse events. The adverse event start date of danger signs or severe malaria will be used in the determination of ETF and LCF. Only *P. Falciparum* asexual form is used for parasitemia/parasite in the assessments of treatment failure and ACPR in [Section 2.1.1.2](#) below. The body temperature assessment closest to the blood smear assessment date will be used.

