2.2 Analysis sets

Randomized set

All patients who are enrolled in the PK run-in cohort or randomized in Parts A and B. Unless otherwise specified, misrandomized patients will be excluded from the randomized set. For the PK run-in part, this set includes all patients with informed consent and treated with study medication.

Misrandomized patients, if identified from IRT, include patients who are screen-failures, but have been randomized by the investigator before eligibility was finally assessed or mistakenly, and have not been treated. If patients were re-screened and successfully randomized, they will be included in the randomized set according to the treatment assigned in the last randomization.

Note: There is no randomization in the PK run-in cohort. For this cohort, the more appropriate terminology is “Enrolled set”. However, ‘Randomized set’ is used for simplicity.

Full analysis set (FAS)

FAS will be comprised of all patients from Randomized set who take at least one dose of study treatment during the treatment period and whose baseline *P. Falciparum* asexual parasitemia count is greater than 0. Following the intent-to-treat principle, patients will be analyzed according to the treatment group assigned to at randomization.

Safety set (SAF)

Safety set includes all patients who take at least one dose of study drug during the treatment period. Patients will be analyzed according to treatment received. In particular, patient will be

analyzed in the same treatment group as randomized if s/he receives at least one dose of the study medication of that group.

Per-protocol set (PPS)

Per-protocol set will be comprised of patients in FAS who

- did not have any important protocol deviations
- took at least 80% of randomized study medication(s). If a patient vomited the original dose but did not vomit the replacement dose, the patient is considered as taking the dose of study medication. Since a partial compliance, such as 83%, etc., can be calculated based on the actual dosage taken (see Section 2.4.1), this allows patients assigned to KAF156 and LUM-SDF arms to take partial dosages which slightly deviates from the protocol.
- did not take non-study drug antimalarial medications prior to Day 29 unless experiencing any treatment failure (ETF, LCF, LPF) (e.g new infections between Day 8 and Day 29), and

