2.5.4 Supportive analyses

The primary efficacy variable will be performed based on the FAS using the statistical method specified in [Section 2.5.2](#).

Primary efficacy variable will be handled additionally for those patients who are excluded from the PPS as follows:

- Presence of parasitemia which cannot be determined to be recrudescence or reinfection due to missing PCR data will be counted as non-responders (from the day of test)
- Missing/underdetermined responses at Day 29 due to missing blood smear data at the visit will be counted as non-responders unless there is a later blood smear test indicating no parasitemia
- Patients who received non-rescue anti-malarial medication will be considered in the analysis as if they had not taken the anti-malarial drug.
 - Note: These patients did not experience any treatment failure (ETF, LFT, or LPF). In case that non-PPS patients who experienced treatment failure, they will be included as non-responders if they received rescue medication for the treatment of *P. falciparum* malaria due to recrudescence or as responder for PCR corrected ACPR if they received rescue medication for treatment of a new infection on Day 8 or later.

For exploratory purpose, 2-sided 95% confidence intervals for the difference in ACPR at Day 29 between each KAF156/LUM-SDF treatment group and Coartem[®] will be constructed using the Wilson uncorrected method.

Let

a = # patients with responders in investigational arm

c = # non-responders in investigational arm

m = sample size of investigational arm ($a+c$)

b = # responder in control arm

d = # in control arm

n = sample size of control arm ($b+d$)

$\theta = \pi_1 - \pi_2$ is the treatment difference

$\hat{\theta} = a/m - b/n$ is estimated treatment difference

Method based on the Wilson score method for the single proportion, without continuity correction:

$L = \hat{\theta} - \delta$, $U = \hat{\theta} + \varepsilon$ where

$$\delta = \sqrt{\{(a/m - l_1)^2 + (u_2 - b/n)^2\}} = z\sqrt{\{l_1(1 - l_1)/m + u_2(1 - u_2)/n\}}$$

$$\varepsilon = \sqrt{\{(u_1 - a/m)^2 + (b/n - l_2)^2\}} = z\sqrt{\{u_1(1 - u_1)/m + l_2(1 - l_2)/n\}}$$

l_1 and u_1 are the roots of $|\pi_1 - a/m| = z\sqrt{\{\pi_1(1 - \pi_1)/m\}}$, and l_2 and u_2 are the roots of $|\pi_2 - b/n| = z\sqrt{\{\pi_2(1 - \pi_2)/n\}}$.

where z is the standard normal deviate associated with 5% level of significance (l.o.s.) two sided.

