5.7 Rule of exclusion criteria of analysis sets

Table 5-10 Protocol deviations and non-PD criteria leading to exclusion from analysis sets

Analysis Set	PD (Description and ID) that causes Patients to be excluded	Non-PD criteria that cause Patients to be excluded
Randomized	
 Informed Consent for study participation or parental consent not obtained and patient entered trial (INCL01) 	
 Not randomized (Parts A and B) Misrandomized if identified from IRT (Parts A and B) Not treated with study medication (PK run-in part)
FAS	NA	
 Not in Randomized set; Baseline parasitemia count is 0 or missing No study drug taken
PPS	
 Parasite specie is other than Plasmodium falciparum OR mixed infection (INCL04) Baseline plasmodium falciparum parasite count <1000/uL or >=150000/uL at screening visit (INCL05) No fever within the past 24 hours at baseline (INCL07) Prohibited non-antimalarial medications that may have effect on efficacy (PROH01b) if received before the Day 29 visit without being treatment failures 	
 Not in FAS; <80% of randomized study medication taken Received non-study concomitant antimalarial drugs prior to Day 29 without experiencing treatment failure Not classified as non-responder before Day 8, no positive blood smear parasite on Day 8 onwards, and blood smear parasite result is missing at Day 29 and later (early discontinued) Not classified as non-responder before Day 8, have at least one positive blood smear parasite result between Day 8 and Day 29 which cannot be determined as recrudescence or new infection based on PCR genotyping and have parasites cleared prior to the positive blood smear parasite;

		
 Not classified as non-responder before Day 8, no positive blood smear parasite before Day 29, blood smear parasite result is missing at Day 29, and blood smear parasite result is not negative at Day 43 (intermediate missing)
SAF	NA	
 Not in Randomized set; No study drug taken
PK	Patients who received concomitant prohibited medication which found to be change in the exposure that impacts interaction in PK parameters; will be reviewed case by case for exclusion from the PK set	
 Not in SAF No evaluable pharmacokinetic parameter data Compliance is <80% of randomized study medication taken

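### The SAP lets drug users stay in the per-protocol set if they have a treatment failure, without saying that the failure must precede the drug or occur by Day 29

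*SAP*

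**What the plan says.** **Protocol 9.1 (PPS).** The antimalarial criterion turns on why the drug was given. A patient qualifies who "did not take other antimalarial medications prior to Day 29 for reasons other than rescue medication given for signs and symptoms of infection". The infection named there is *P. falciparum*, and an unsatisfactory effect of treatment is the other accepted reason. Later outcome plays no part. Important protocol deviations exclude without condition; the clinical team identifies them before each lock.

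**SAP 2.2 (PPS).** The antimalarial criterion turns on whether the patient failed: "did not take non-study drug antimalarial medications prior to Day 29 unless experiencing any treatment failure (ETF, LCF, LPF"). The example given is a new infection between Day 8 and Day 29.

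**SAP 5.7, Table 5-10 (PPS).** The row for outside antimalarials reads "Received non-study concomitant antimalarial drugs prior to Day 29 without experiencing treatment failure". The row for prohibited drugs reads "Prohibited non-antimalarial medications that may have effect on efficacy (PROH01b) if received before the Day 29 visit without being treatment failures".

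**SAP 2.5.4.** On users of non-rescue antimalarials who are outside the PPS: "Note: These patients did not experience any treatment failure (ETF, LFT, or LPF").

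**SAP 2.1.1.1.** Late failure extends past the primary time point. Late parasitological failure covers "Presence of parasitemia on any day from Day 8 to Day 43 and axillary temperature" below the fever threshold; late clinical failure also runs to Day 43.

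**SAP 2.4.2.** Rescue is separated from other antimalarial use by order: use after study drug was stopped for a failure is rescue, anything else is not. The PPS criterion does not refer to this distinction.

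**SAP 2.5.2 and Protocol Table 3-2.** The PPS carries the hypothesis test for each combination in each part. The same limit, a lower 95% exact bound above 80%, is the efficacy hurdle for entry to Part B.

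**SAP section 4.** No changes to protocol-specified analyses are declared.

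**The concern.** An analysis set should not depend on the outcome it is used to estimate. Under the literal SAP wording it can, in two ways.

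1. *Drug first, failure later.* A patient takes an outside antimalarial or a PROH01b drug on, say, Day 6 for another illness. If he recrudesces on Day 20 he stays and counts as a non-responder. If he is cured he is removed. This pushes the rate down.
2. *Failure after the endpoint.* A user is film-negative on Day 29 and parasitaemic on Day 43. He has had a late failure, so he is exempt; he meets the evaluability criterion and counts as a Day 29 responder. The same user without the Day 43 parasitaemia is removed. This pushes the rate up.

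The SAP rule also drops a patient given an antimalarial for poor response in whom no formal failure was recorded. The protocol keeps that patient, because the drug was rescue.

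At stake is the pass or fail of an arm near the 80% limit, and so which regimens go into Part B.

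**Working it through.** **1. The plan's own figures reproduce.** The lower Clopper-Pearson limit exceeds 80% at n = 41 with 38 or more responders and at n = 42 with 39 or more. At a true rate of 95%, exact binomial power is 85.3% and 84.3%, in line with the stated 80% or more. At a true 80%, the rejection probability at n = 42 is 2.1%. Sizes also agree: 50 × 0.84 = 42, 25 × 0.84 = 21, and 6 × 50 + 25 = 325.

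**2. Expected rate under the first path.** Let p be the true PCR-corrected rate, u the share of users, and q the share of otherwise cured users who clear parasites and are then reinfected. Reinfected users have a formal failure, so they stay in the PPS, but they count as PCR-corrected responders. Assume that the drug does not change the outcome.

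- Kept responders: (1 − u)p + u·p·q
- Kept failures: (1 − u)(1 − p) + u(1 − p) = 1 − p
- Expected PPS rate: [(1 − u)p + u·p·q] / [(1 − u)p + u·p·q + (1 − p)]

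The documents give no value for u or q. The range below is an assumption.

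| p = 95% | u = 5% | u = 10% | u = 20% |
|---|---|---|---|
| Literal SAP rule, q = 0 | 94.8% | 94.5% | 93.8% |
| Literal SAP rule, q = 0.5 | 94.9% | 94.8% | 94.5% |
| Exclude users whatever the outcome | 95.0% | 95.0% | 95.0% |

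Example: u = 10%, q = 0 gives 0.855/(0.855 + 0.05) = 0.9448. The shift is about 0.3 to 1.2 points at q = 0 and 0.1 to 0.5 points at q = 0.5.

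**3. Power, with 42 evaluable patients before the rule, p = 95%, q = 0.**

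| | u = 5% | u = 10% | u = 20% |
|---|---|---|---|
| Literal SAP rule | 72.9% | 66.2% | 53.6% |
| Exclude users whatever the outcome | 74.9% | 71.4% | 64.0% |

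The cost of tying exclusion to outcome is the difference between the rows, about 2 to 10 points. The rest of the fall from 84.3% comes from the smaller set, which any exclusion rule causes.

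**4. Error rate at a true 80%.** With q = 0 the rejection probability under the literal rule is 1.2%, 0.7% and 0.4% for u = 5%, 10% and 20%, below the 2.1% for all 42 patients. On these assumptions the first path does not inflate type I error.

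**5. One patient near the limit.**

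| Situation | Literal SAP rule | User excluded |
|---|---|---|
| One failing user kept (first path) | 40/44, lower limit 78.3%, not met | 40/43, 80.9%, met |
| One Day 29-negative, Day 43-positive user kept (second path) | 38/41, 80.1%, met | 37/40, 79.6%, not met |

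An arm of 42 shows the same: 38 non-users with 2 failures, plus 4 users of whom 1 recrudesces and 3 are cured. The literal rule gives 36/39, lower limit 79.1% (not met). Excluding all users gives 36/38, 82.3% (met). Keeping all users gives 39/42, 80.5% (met).

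**6. How often.** With 42 patients, 10% users and 5% failures, the expected number of failing users kept is 42 × 0.10 × 0.05 = 0.21 per arm. The documents give no basis for a frequency of the second path.

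**The case against.** The strongest reply is that the SAP is silent on order and does not decree that order is irrelevant. Table 5-10 can be read as failure status at the time the drug was received, the SAP 2.2 example is a failure inside the Day 29 window, and SAP 2.4.2 already defines rescue by order. On that reading both paths disappear. This stands in part: a reader might infer that the SAP deliberately exempts every failing user whatever the sequence, and no text says so. But the SAP 2.5.4 note describes non-rescue users outside the PPS as patients with no failure at all, which fits the ever-failed reading, and a programmer needs one rule.

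A reader might also infer that the PROH01b exemption can have no rationale. On the time-of-receipt reading it has one: a drug taken after failure cannot change an outcome already fixed. Nor does the protocol set a PROH01b rule; the departure from its reason-based criterion concerns antimalarials only.

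The size is fairly challenged too. The documents prohibit outside antimalarials during the study, keep patients in hospital to Day 4 and assume 16% PPS exclusions for all causes, so a 20% user share is hard to square with the plan. The one-patient cases show how discrete the exact test is, not how often the problem arises.

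Mitigation exists. The supportive full-analysis-set analysis applies the same exact test and keeps non-rescue users whatever their outcome. The Kaplan-Meier analysis censors users at first drug use, but only those who are not non-responders. The sensitivity analysis in SAP 2.7.2.2 concerns uncorrected ACPR. None of these carries the primary test.

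**Conclusion.** The point holds as a gap in the PPS rule that should be closed. SAP 2.2 and both Table 5-10 rows tie drug exclusions to failure without fixing its order or its time limit, so membership of the primary set can depend on outcome. For antimalarials this also departs from the protocol without being declared.

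The expected effect is small: about 0.3 to 1.2 points off a true 95% for an assumed 5–20% users, none reinfected and outcome unaffected by the drug, and less with reinfection. It usually works against the study drug. The second path works the other way, and its frequency cannot be estimated from the documents.

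A reader might infer that the rule favours the study drug overall, or that it distorts arms differently through transmission setting. The documents support neither. The quantified path is conservative, and randomization stratified by country within each part balances transmission across arms by design.

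**What to change.** In SAP 2.2 and both Table 5-10 rows, state that:

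- (a) an antimalarial given as rescue for signs and symptoms of *P. falciparum* infection or for unsatisfactory therapeutic effect (Protocol 9.1), or any antimalarial or PROH01b drug started on or after the date a failure criterion was first met, does not exclude;
- (b) any other non-study antimalarial taken before Day 29, or PROH01b drug taken before the Day 29 visit, excludes regardless of later outcome;
- (c) a failure first occurring after the Day 29 assessment creates no exemption.

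List the change in SAP section 4.

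The rescue clause in (a) is needed. Excluding every antimalarial started before a formal failure would remove patients rescued for poor response, whom the protocol keeps, and would bias the rate upward. The SAP should also say how rescued patients kept without a formal failure are scored in the PPS; for the full analysis set, Protocol 9.4.4 counts rescue for *P. falciparum*, other than for a new infection, as failure.

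Cost: a few lines of text, a date comparison and a reason-for-use check in the PPS program. A few patients change set.

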2.2.1 Subgroup of interest

The following subgroups will be used for descriptive summary of the selected efficacy and safety analyses . The details will be provided in the corresponding sections.

- Age groups as per section 2.3
- Baseline weight groups as per section 2.3
- Sex (male vs female)
- Region

2.3 Patient disposition, demographics and other baseline characteristics

2.3.1 Medical history

Any condition entered on the *Relevant medical history / current medical conditions* CRF will be coded using the MedDRA dictionary. They will be summarized by system organ class (SOC) and preferred term (PT) of the MedDRA dictionary. Summary will also be provided on medical conditions that were active at the time of screening.

Medical conditions that are present after informed consent has been signed are collected in the Adverse event panel and will be summarized separately from adverse events.

The Medical History conditions captured on the eCRF “Protocol solicited medical history or medical history possibly contributing to liver dysfunction” will be tabulated separately.

History of use of alcohol will also be provided.

Unless otherwise specified, analyses will be based on the randomized set.

2.3.2 Patient demographics and other baseline characteristics

Demographic data and baseline disease characteristics will be descriptively presented and tabulated per treatment group, as well as overall, using randomized set and PPS. If many patients are excluded from randomized set, summary will also be provided for the FAS.

Following demographic variables will be summarized

- Age and age categories (for Part B: 2 to <6, 6 to <12 ; for PK run-in cohort and and Part A: <12, 12 to <18, 18 to <65, and ≥ 65 , <18 vs ≥ 18 yrs)
- Sex (male, female)
- Patient child bearing status (able to bear children, premenarche, post menopausal, sterile of child bearing age)
- Race (Caucasian, black, Asian, native american, pacific islander, unknown, other)
- Ethnicity
- Body weight and weight categories (<35, 35 to <75 and ≥ 75 kg for Part A and PK run-in cohort); (10 to <15, 15 to <25, 25 to <35 and ≥ 35 kg for Part B);(<15 , 15 to <25, 25 to <35, 35 to 75, >75 kg for Parts A+B)
- Body height (cm)
- BMI and BMI categories (<16, 16 to 25, >25) (Kg/m^2)

Following disease characteristics at baseline will be summarized

- Body temperature and categories (<37.5, 37.5 to <39, ≥ 39) ($^{\circ}\text{C}$) for (*axillary*) and <38.0 $^{\circ}\text{C}$, 38.0 to 39.5, ≥ 39.5 for other routes)

- Falciparum species: (P. Falciparum asexual forms, P. Falciparum gametocytes, P. Vivax, P. Ovale, P. malariae, P. Knowlesi, and Mixed-infection , n (%))
- P. falciparum density per micro ltr. and its categories (<1,000, 1,000 to <2,000, 2,000 to <5,000, 5,000 to <15,000, 15,000 to <50,000, 50,000 to <100,000, 100,000 to <150,000, >=150,000 parasites/ μ L; <100,000 / μ L, \geq 100,000 parasites / μ L)
- Gametocytes counts / μ L.

2.3.3 Patient disposition

The number of patients who screened and screening failures will be presented. In addition, the reasons for screen failures will be provided. The number and percent of patients who completed each epoch (treatment and follow up) and who discontinued each epoch prematurely (including the reason for discontinuation) will be presented for each treatment group and overall.

For each protocol deviation, the number and percent of patients for whom the deviation applies will be tabulated.

Randomized set will be used.

2.4 Treatments (study treatment, rescue medication, concomitant therapies, compliance)

2.4.1 Study treatment / compliance

Number and percent of doses taken will be presented by treatment group and drug (KAF156, LUM-SDF, or Coartem[®]). The percentage will be calculated based on the planned number of doses per treatment group.

Planned number of doses in a treatment group = planned number of days of dosing x number of doses to be administered per day in that treatment group.

For example, planned number of doses is 3 for 'KAF156 400 mg and LUM-SDF 480 mg QD for 3 days' group, 6 for Coartem, etc.

In the percent calculation for KAF156/LUM-SDF based treatment groups, patient is considered to be dosed if s/he took any study drug regardless of vomiting or not.

Percent of doses taken (i.e. compliance) on a day will be calculated as actual dose administered /planned dose x 100% capped at 100% (if a compliance on a given day exceeds 100%, use 100%). Average compliance for a study drug will be calculated as sum of the compliance for all days and divide by the number of day's. For KAF/LUM, compliance for combined dose will be the average compliance of both drugs.

In addition, percent of full doses taken will be calculated as actual number of full doses administered /planned number of doses x 100% where a patient is considered to be fully dosed if s/he took all study drug(s) in full dose.

Compliance will be categorized by < 80 % and \geq 80 % of full doses taken and summarized by treatment group.

Number and percent of patients with study drug vomiting and dose replacement will be presented by treatment group.

Average daily dosage and total dosage (in mg) of each study drug (KAF156, LUM-SDF, Artemether, Lumefantrine) will be summarized by treatment group. If a patient vomited the original dose and took a replacement dose, the replacement dose will be used to calculate the average.

Average daily dosage = sum of actual doses taken in mg / **planned number of days of treatment**.

For Coartem, the tablets taken by the patient are converted into mg based on the strength of tablet.

Note- If a patient vomited the original dose but did not vomit the replacement dose, the patient is considered as fully dosed. If a patient vomited the original dose and did not have a replacement dose or vomited both the original dose and the replacement dose, the patient is not considered as fully dosed.

Safety set will be used.

